12.2.2 Efficacy Population

The Efficacy Population will consist of all subjects of the Safety Population who have a baseline and at least 1 post-baseline assessment of 1 or more of the secondary efficacy outcome measures.

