4.2 Efficacy Population

The Efficacy Population will consist of all subjects of the Safety Population who have a baseline and at least 1 post-baseline assessment of 1 or more of the secondary efficacy outcome measures. Subjects that dropout or withdraw prior to Day 14 will be replaced in the efficacy population. For the efficacy evaluations, subjects will be analyzed according to the treatment actually received. Any subjects that began the study administering the treatment for one of the study arms and then later in error switched treatments to another study arm will not be included in the efficacy population.

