9. EFFICACY EVALUATION

9.1 Overview of Efficacy Analysis Issues

9.1.1 Handling of Dropouts and Missing Data

Subjects that dropout or are withdrawn prior to Day 14 will be replaced in the Efficacy Population. The mixed models analyses (described in the sections below) will automatically adjust for any missing values provided the missing values are missing at random; and thus, no additional imputation is necessary for missing values that are missing at random.

Missing observations are “not missing at random” if their missing-ness is possibly correlated with disease progression or efficacy. Missing efficacy observations due to missed visits or early study withdrawal will be deemed “not missing at random” if there were any treatment-emergent AE (TEAE) prior to or concurrent with a subject’s missed visit and the relationship between the TEAE and study drug was rated as “Possible”, “Probable”, or “Definite”.

If more than 5% of a given efficacy endpoint is missing, or any missing observations are deemed “missing not at random” then a sensitivity analysis will be performed by repeating the given efficacy analysis with all missing values imputed using “last observation carried forward”. The sensitivity analysis will also be triggered if for any other reason the principle investigator suspects that missing values may bias the analysis. The reasons any sensitivity analyses are triggered will be footnoted in the sensitivity analysis tables.

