9.2.2 Secondary Efficacy Endpoints

At baseline, study Day 14, and study Day 28, the following secondary efficacy variables: modified gingival index (MGI), bleeding on probing (BOP), IL-1 β , plaque index (PI), plaque severity index (PSI) and gingivitis severity index (GSI) will be recorded. PI, MGI, and BOP will be scored for each of the 6 tooth-sites for each tooth. IL-1 β will be measured in the GCF collected from one tooth (assigned by algorithm) in each quadrant. All efficacy analyses will be performed on the Efficacy Population.

The time point of greatest interest would be Day 28, but analysis will also be performed for Day 14.

The exploratory analysis pocket depth (PD) and clinical attachment level (CAL) will be descriptive.

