9.3.2 Secondary Efficacy Analyses

The main objectives of the secondary efficacy analyses are to: 1) obtain some evidence of efficacy (either a statistically significant effect or a trend); 2) obtain estimates of the size and variance of possible treatment effects that can then be used to plan later clinical trials; and 3) explore which of several outcomes may best be used to measure efficacy. All efficacy analyses will be based on the efficacy population.

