Since this is a safety phase 1 / 2 with safety measures as the primary endpoints, the secondary efficacy endpoints will not be adjusted for multiplicity. However, the contrast between the treatment and placebo rinse arms with respect to the MGI change from baseline at Day 28 will be considered the secondary endpoint of chief importance. The same statistical contrast but with BOP change from baseline as the dependent variable will be considered the statistical contrast next in order of importance.

Tables will summarize the p-values, contrasts, and least squares means (with standard errors) of the change from baseline and their differences among the treatment groups and visits for each of the mixed models analyses described above.

Summary statistics of the secondary endpoints and their change from baseline, including n, means, minimums, maximums, standard deviations, and standard errors, will be summarized in a table by study arm and study visit. Raw values of all the secondary efficacy endpoints, both on the tooth-site level and the subject level will be listed.

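### SAP 4.2 analyzes efficacy by product received and drops error switchers, and no planned analysis keeps subjects in their randomized arms

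*SAP*

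**What the plan says.** SAP 4.2 sets two rules. First, "For the efficacy evaluations, subjects will be analyzed according to the treatment actually received", so a subject who used the wrong product from the start is counted in the arm of that product. Second, a subject who began on one arm's treatment and later in error "switched treatments to another study arm will not be included in the efficacy population".

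SAP 9.2.2 applies this set throughout: "All efficacy analyses will be performed on the Efficacy Population". SAP 9.3.2 repeats it: "All efficacy analyses will be based on the efficacy population". SAP 9.3.2.1 singles out the test-versus-placebo contrast "with respect to the MGI change from baseline at Day 28 will be considered the secondary endpoint of chief importance". Next in order comes this: "The same statistical contrast but with BOP change from baseline as the dependent variable".

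Protocol 12.2.2 contains neither rule: "The Efficacy Population will consist of all subjects of the Safety Population who have a baseline and at least 1 post-baseline assessment" of at least one secondary efficacy measure. It does not say in which arm a subject is analyzed. SAP 11 declares that wrong-treatment handling was added, so the SAP filled a gap and did not contradict the protocol.

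**The concern.** Both rules depend on what happens after randomization. One moves a subject to another arm and the other removes the subject. Randomization protects a comparison only while subjects stay in the arms to which they were allocated. If misdispensed subjects differ in outcome from the rest of their arm, the contrast picks up that difference as if it were a treatment effect.

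The point is limited to errors that affect subjects who are in, or are moved into, the two rinse arms. Excluding a no-rinse subject who later switched leaves both rinse arms as they were.

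The stake is the credibility of the Day 28 MGI and BOP contrasts. One stated purpose of these analyses is to supply effect sizes for later trials (Protocol 12.5.2, SAP 9.3.2), and a planner should be able to see whether an estimate depends on how errors were handled.

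**Working it through.** **1. Does any planned efficacy analysis restore the randomized arms?**

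- SAP 9.1.1 calls for "repeating the given efficacy analysis with all missing values imputed using" last observation carried forward. This deals with missing values only.
- SAP 9.3.2.2 removes subjects with periodontitis.
- SAP 9.3.3 compares GEE with the mixed model. This changes the estimation method, not the arms.
- SAP 5.1 and 5.2 tabulate disposition and deviations by allocation. These are counts, not effect estimates.

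None of them does.

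**2. Inputs (Protocol 12.3, SAP 2.5).** MGI SD 0.3 at each visit, within-subject correlation 0.3, effect 0.2, alpha 0.05 (taken as two-sided) and 40 completers per rinse arm.

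**3. The plan's own power.** SD of change = 0.3 × √(2 × (1 − 0.3)) = 0.355. SE = 0.355 × √(2/40) = 0.0794, and 0.2/0.0794 = 2.52. This gives 71.2% power, against 70.9% stated. For 40 versus 20 it gives 53.9%, against 53.8% stated. The plan reproduces. Because the analysis model adjusts for baseline, I also use the adjusted SD, 0.3 × √(1 − 0.3²) = 0.286.

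**4. Shift in the MGI contrast with no true effect.** The documents give neither error counts nor prognosis, so both are assumed: k of 40 subjects in one rinse arm, each d SDs worse than the arm average.

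- Excluded: shift = d × SD × k/(40 − k), with SE = SD × √(1/(40 − k) + 1/40).
- Re-assigned to the other rinse arm: shift = d × SD × [k/(40 − k) + k/(40 + k)], with SE = SD × √(1/(40 − k) + 1/(40 + k)).
- Type I error = P(|Z + shift/SE| > 1.96).

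Example, k = 4 re-assigned, d = 1: 4/36 + 4/44 = 0.202. The shift is 0.202 × 0.286 = 0.058, or 0.202 × 0.355 = 0.072. In SE units it is 0.202/√(1/36 + 1/44) = 0.899, so the type I error is 14.6%.

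| Rule | d | k | Shift (SD 0.286 to 0.355) | Type I error |
|---|---|---|---|---|
| Excluded | 1 | 2 | 0.015–0.019 | 5.6% |
| Excluded | 1 | 4 | 0.032–0.039 | 7.7% |
| Re-assigned | 1 | 2 | 0.029–0.036 | 7.3% |
| Re-assigned | 1 | 4 | 0.058–0.072 | 14.6% |
| Re-assigned | 0.5 | 2 | 0.014–0.018 | 5.6% |
| Re-assigned | 0.5 | 4 | 0.029–0.036 | 7.3% |

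If no-rinse subjects 1 SD worse than the rinse-arm mean are moved into one rinse arm, the shift is SD × k/(40 + k): 0.014–0.017 (5.5%) for k = 2 and 0.026–0.032 (7.0%) for k = 4. The documents give no SD for BOP, so no BOP figure can be derived.

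**5. Power when errors occur (SD 0.355, effect 0.2 in those who use the test rinse).** Half-period switchers are assumed to carry half the effect.

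| Errors | As-randomized effect | As randomized, k = 2 / 4 | SAP 4.2, k = 2 / 4 |
|---|---|---|---|
| Whole course, k per rinse arm | 0.2 × (1 − 2k/40) | 62.1% / 52.2% | 71.2% / 71.2% |
| Whole course, one direction | 0.2 × (1 − k/40) | 66.8% / 62.1% | 71.1% / 70.8% |
| Half period, k per rinse arm | 0.2 × (1 − k/40) | 66.8% / 62.1% | 69.0% / 66.7% |
| Half period, one arm | 0.2 × (1 − k/80) | 69.0% / 66.8% | 70.1% / 68.9% |

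SAP 4.2 re-assigns whole-course errors (40 per arm when balanced, 40 + k and 40 − k when in one direction) and excludes switchers (40 − k in each affected arm).

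**The case against.** The strongest reply is that the harm needs errors that track prognosis, and the plan makes those unlikely. The rinses match in color, appearance and taste (Protocol 6.1.2). Examiners and rinse subjects are masked (5.4.2), and products are segregated with numbers recorded (6.4). The study blind is broken after database lock (SAP 2.4), apart from an individual code break for a serious event and possible unblinding of the medical monitor or DSMB (Protocol 9.5). If errors hit subjects at random, both SAP rules are unbiased. Two or four randomly chosen subjects would average at least 1 SD worse with probability of only about 8% or 2% (1 − Φ(√2) and 1 − Φ(2)), so the conditional type I error rates above are not the operating rate of the planned test.

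That stands, and so do three further points:

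- Efficacy is preliminary, without multiplicity control and not fully powered. For those aims, the effect of the product actually used is a defensible target.
- As-randomized analysis dilutes the effect whenever errors occur, whereas its benefit appears only if the errors also relate to prognosis.
- The remedy does not fully restore the randomized set, because the post-baseline requirement and the replacement of subjects who leave before Day 14 remain.

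These points limit priority. They do not explain why no as-randomized estimate is planned at all. The SAP itself foresees these errors, rinse is supplied at up to five visits, and the allocation tables would show that errors occurred but not what they did to the contrast.

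**Conclusion.** The concern holds. Followed as written, SAP 4.2 would produce Day 28 MGI and BOP contrasts that are not comparisons of randomized groups if wrong-product errors involve the rinse arms, with no as-randomized estimate beside them.

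The tabulated shifts rest on assumed error counts, poor prognosis in the affected subjects and errors in one direction. They are unfavorable cases, not expected values. The effect is zero if no errors occur or if affected subjects are typical of their arm, and it cancels if errors are balanced between the rinse arms with similar prognosis. The change is recommended, not required.

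**What to change.** Replace the last two sentences of SAP 4.2 with:

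> For efficacy, subjects in the Efficacy Population are analyzed in the arm to which they were randomized, regardless of product received; subjects who switched product in error remain in their randomized arm.

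Keep treatment received for safety (SAP 4.1). If any wrong-product error occurs, also report the treatment-received, switch-excluded result as supportive. Call the set modified as-randomized, because the post-baseline and replacement rules stay.

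If the sponsor prefers to keep SAP 4.2 as the main analysis, the minimum is to pre-specify as-randomized Day 28 test-versus-placebo contrasts for MGI and BOP and report them beside it whenever an error occurs.

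Either version should be settled before database lock and unblinding, so that it is not post hoc. The full change costs two sentences and no new data, plus the power loss in step 5 of the working if errors occur. The minimum option has no power cost in the main analysis.

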5. STUDY SUBJECTS

5.1 Disposition of Subjects

The disposition of all subjects and the study populations to which they belong will be presented in the subject listings and summarized in a table as counts by treatment allocation. The subject dispositions will include subjects randomized, completing the study, discontinuing/ withdrawing, and the number of subjects in both the safety and efficacy analysis populations. The reasons for discontinuing/ withdrawing from the study will be included in the disposition listing and table.

5.2 Protocol Deviations

Protocol deviations will be presented in a listing and summarized in a table by treatment allocation and type of deviation. Types of deviations that will be summarized as counts and percentages in the table include:

- Consent deviation
- Eligibility deviation
- Missed visit
- Procedure performed outside of visit window
- Study procedure not completed
- Study procedure deviation
- Other

Table 5.2.1 Assessment Time Windows

Study Visit	Time window (study day \pm assessment window)
Visit 1 – Enrollment, Baseline	Day 0
Visit 2	Day 3 \pm 1
Visit 3	Day 7 \pm 1
Visit 4	Day 14 \pm 1
Visit 5	Day 21 \pm 1
Visit 6 – Final Study Visit	Day 28 \pm 1
Visit 7 – Telephone Safety Follow-up	Day 90 \pm 14

6. DEMOGRAPHIC AND OTHER BASELINE CHARACTERISTICS

Baseline data (e.g., demography, medical history, dental history, and concurrent medications) will be summarized.

Demographic baseline characteristics will be summarized descriptively for both the Safety and Efficacy Populations. The demographic variables of sex, age, ethnicity, and race will be listed and summarized in a table. The categorical variables of sex, ethnicity, and race will be summarized by frequencies. Age will be summarized as mean, SD, median, minimum, and maximum.

To assess overall health of the study participants prior to study treatment, any significant medical history will be included in the subject listings. The number and percentage of subjects with each medical history event will be presented by body system or oral structure.

Results of the baseline oral exam will be listed by area/oral structure examined and will denote an abnormal or normal result; and, if abnormal, the associated description of the abnormality will be listed.

Tooth status at baseline will be presented in a listing by subject and tooth, and will denote whether the tooth is missing, sound, decayed, filled, fractured, was crowned, and/or is a dental implant.

All prior and concomitant medications will be coded to preferred drug names and therapeutic drug class using the WHO Drug Dictionary. Use of concomitant medications will be summarized for each therapeutic drug class and each preferred drug name. Concomitant medications will include medications reported on the Concomitant Medications page of the CRF.

7. MEASUREMENTS OF TREATMENT COMPLIANCE

Compliance will be recorded at all study visits by measurement of the volume of remaining product. Expected volume returned is calculated as the volume dispensed - (number of days since last study visit x 30ml). A subject will have “over used” the rinse if the percent volume used is > 120%. A subject will have “under used” the rinse if the percent volume used is < 80%. A subject listing will capture under- and over-usage of study drug and non-compliance as determined by the volume of returned study drug and as reported by the subject queries. If more than 12 subjects are out of study drug compliance, a table will summarize the frequencies of under- and over-usage of study drug by treatment arm.

8. SAFETY EVALUATION

8.1 Overview of Safety Analysis Methods

All safety analyses will be carried out using the Safety Population.

- Adverse events (AEs)
- Unanticipated problems
- Vital signs
- Laboratory determinations (hematology, serum chemistry, and urinalysis)
- Physical examinations
- Dental examinations

With the exception of the progression of periodontitis based on the dental examinations, no statistical comparisons between the treatment groups are planned for the safety variables.

8.2 Progression of Periodontitis

Progression of periodontitis will be defined as an increase of 2 mm or more in pocket depth (PD) or clinical attachment level (CAL) from the Day 0 baseline measurement. The frequency (percent) of subjects with progression of periodontitis will be summarized by study arm, visit, and overall. Generalized linear mixed models regression based on a binomial distribution and logit link will compare the odds ratios of the overall incidence of the progression of periodontitis among the study arms at the Day 14 and Day 28 time points. The results of the generalized linear mixed model will be presented in a table and include p-values and odds ratios (with 95% CI) for the treatment arm comparisons at the two study visits. The p-values will not be adjusted for multiplicity.

The generalized linear mixed models analyses will automatically adjust for any missing values provided the missing values are missing at random; and thus, no additional imputation is necessary for missing values that are missing at random.

Missing observations are “not missing at random” if their missing-ness is possibly correlated with disease progression or efficacy. Missing PD or CAL observations due to missed visits or early study withdrawal will be deemed “not missing at random” if there were any treatment-emergent AE (TEAE) prior to or concurrent with a subject’s missed visit and the relationship between the TEAE and study drug was rated as “Possible”, “Probable”, or “Definite”.

If more than 5% of the PD or CAL measures are missing, or any missing PD or CAL measures are deemed “not missing are random”, then a sensitivity analysis will be performed by repeating the above generalized linear mixed model with all missing values imputed as having progression of periodontitis. The sensitivity analysis will also be triggered if for any other reason the principal investigator suspects that missing values may bias the analysis. The reasons a sensitivity analysis is triggered will be footnoted in the sensitivity analysis table.

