2.5 Potential Risks and Benefits

2.5.1 Potential Risks

BLXA4-ME topical oral rinse is intended for administration as an oral rinse (mouthwash) and is not intended for ingestion. For this study, BLXA4-ME will be applied topically as an oral rinse that will be held in the mouth for 45 seconds each day for 28 days. Potential risks include oral irritation from use of the rinse. In a preclinical 28-day oral irritancy study in rats with abraded oral mucosa, transient erythema and edema of the oral mucosa were noted in animals treated with either BLXA4-ME or a saline solution used as a control. Microscopic examination of oral tissues showed no differences between rats treated with BLXA4-ME and control rats treated with saline. In this Phase 1/2 safety study, oral tissues will be closely monitored for signs of inflammation and irritancy, and product administration will be discontinued if toxicity develops. Because the investigational compound may be absorbed through the oral mucosa, blood and urine for safety laboratory tests will be collected from all subjects at screening and 14 and 28 days after initial product administration. Treatment of gingivitis has the potential to conceal the presence of the more serious condition of periodontitis; therefore, subjects will be monitored for development or progression of periodontitis, using clinical periodontal measurements. In addition, oral flora will be analyzed to detect any increase in pathogenic organisms.

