8.1.2 Clinical Periodontal Measurements

The clinical periodontal measurements described below will be obtained from the full mouth at Baseline and on Days 14 and 28. In addition, plaque and gingivitis severity scores will be calculated using the method described in ([Panagakos, Volpe et al. 2005](#)). These severity scores represent the ratio of surfaces with high PI (scores 2 and 3 assessed with the Silness and Løe PI) and high gingival index (scores 3 and 4 assessed with the MGI) to total scored surfaces.

- Modified gingival index ([Gordon, Lamster et al. 1985](#)): The MGI will be assessed at 6 sites per tooth (mesiobuccal, buccal, distobuccal, distolingual, lingual, and mesiolingual aspects of the tooth), and will be recorded as follows:
 - 0 = absence of inflammation
 - 1 = mild inflammation; slight change in color, little change in texture of any portion of, but not the entire, marginal or papillary gingival unit
 - 2 = mild inflammation; criteria as above but involving the entire marginal and papillary gingival unit

- 3 = moderate inflammation; glazing, redness, edema, and/or hypertrophy of the marginal or papillary gingival unit
- 4 = severe inflammation; marked redness, edema, and/or hypertrophy of the marginal or papillary gingival unit; spontaneous bleeding, congestion, or ulceration
- Probing depth: Periodontal pocket depth will be determined at 6 sites per tooth using a UNC-15 periodontal probe, with measurements rounded to the next lower whole millimeter.
 - Distance from free gingival margin to cementoenamel junction: The GM-CEJ will be measured to calculate the CAL. The GM-CEJ is measured with a periodontal probe at 6 sites per tooth, and is recorded in millimeters rounded to the next lower whole number. Millimeters of recession will be recorded as a negative number, and when the free gingival margin is coronal to the cementoenamel junction, the GM-CEJ will be recorded as a positive number.
 - Clinical attachment level: The CAL will be calculated by subtracting the GM-CEJ from the PD.
 - Bleeding on probing: BOP is a dichotomous measurement that will be recorded at the same 6 sites per tooth:
 - 0 = no bleeding in 15 seconds after probing
 - 1 = bleeding in 15 seconds after probing
 - Plaque index ([Silness and Loe 1964](#)): Plaque will be assessed at 6 sites per tooth (mesiobuccal, buccal, distobuccal, distolingual, lingual, and mesiolingual aspects of the tooth). The PI will be recorded as follows:
 - 0 = no plaque

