12.5 Final Analysis Plan

12.5.1 Primary Safety Analysis

Safety data will be summarized for all subjects in the Safety Population. Adverse event and SAE reporting requirements are found in Section 9.

Safety for study treatment groups will be evaluated by the incidence, severity, and type of AEs, and by changes from baseline in subjects' oral examination findings, vital signs, and clinical laboratory test results. Concomitant medications taken during the trial will be summarized and listed.

The number and percentage of subjects who experience an AE, SAE, treatment-related AE, treatment-related SAE, and AE leading to discontinuation from the study will be summarized. All AEs will be coded by system organ class and preferred term according to the terminology of the Medical Dictionary for Regulatory Activities, and severity will be graded according to the National Cancer Institute's CTCAE, Version 4.0.

All AEs will be summarized by system organ class and preferred term and by maximum CTCAE severity grade. Summaries will also be presented by relationship to study treatment. For AE summaries, emphasis will be placed on the summary of treatment-emergent AEs, defined as new AEs reported after initiation of treatment or pre-existing conditions that worsen during the treatment period.

Subjects who withdraw from study treatment because of an AE will be listed.

The incidence of development or progression of periodontal disease at Day 28 will be reported for each study arm as part of the primary safety analysis. Development of disease or progression of existing periodontitis is defined as an increase from baseline of 2 mm or more in either the PD or CAL measures.

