9.2.3.2 Clinical Attachment Loss

The clinical attachment level (CAL) will be calculated at each of the 6 tooth-sites for each tooth of each participant during the baseline and study Day 28 visit. CAL will be calculated as PD minus the cementoenamel junction.

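### SAP 8.2 compares arms only on a combined PD-or-CAL progression outcome, although events met by PD alone always carry a recorded gingival margin shift that may follow the rinse's intended effect; the components should be reported separately

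*SAP*

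**What the plan says.** Protocol 3.2.1, 8.1.2 and 12.5.1 use one rule for development or progression of periodontitis. In 12.5.1 it is "an increase from baseline of 2 mm or more in either the PD or CAL measures". SAP 8.2 repeats it as "an increase of 2 mm or more in pocket depth (PD) or clinical attachment level (CAL") from Day 0. A PD rise therefore counts the same as a CAL rise.

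Protocol 8.1.2 links the two measures: "The CAL will be calculated by subtracting the GM-CEJ from the PD". Recession is recorded as negative, and "when the free gingival margin is coronal to the cementoenamel junction, the GM-CEJ will be recorded as a positive number". Both PD and GM-CEJ are rounded down to whole millimeters. SAP 9.2.3.2 gives a shortened version, "CAL will be calculated as PD minus the cementoenamel junction", which I read as the same formula.

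Progression belongs to the primary safety outcome (Protocol 3.2.1). SAP 8.1 makes it the only safety variable with a planned statistical comparison between arms. SAP 8.2 tabulates the combined event by arm and visit, and fits a logit generalized linear mixed model giving odds ratios, 95% confidence intervals and unadjusted p-values at Days 14 and 28. It does not separate events met on CAL from events met on PD alone. SAP 9.3.3 analyses PD and CAL separately, but as change at Day 28.

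Protocol 2.5.1 explains why the outcome is collected: "Treatment of gingivitis has the potential to conceal the presence of the more serious condition of periodontitis".

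**The concern.** PD is measured from the gingival margin, and CAL removes the margin's position by construction. The PD limb can therefore respond to movement of the margin, which the CAL limb is built to exclude.

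Margin position is not neutral in this trial. Protocol 8.1.2 defines MGI grade 3 as "moderate inflammation; glazing, redness, edema, and/or hypertrophy of the marginal or papillary gingival unit", and grade 4 by marked forms of the same signs. SAP 9.2.1 and 9.3.2.1 make MGI change at Day 28 the efficacy comparison of chief importance. If the rinse reduces marginal swelling, PD-only events may become less frequent in the active arm whatever happens to attachment. A null or favourable composite odds ratio could then reflect attachment, margin position or both, and the planned output would not show which. The outcome was included to guard against gingivitis treatment hiding periodontitis, so the reader needs to be able to tell.

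**Working it through.** The documents give no event rate, power or margin for progression, so there is no stated figure to reproduce. The check has four steps.

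**1. Identity for recorded values.** From Protocol 8.1.2, CAL = PD − GM-CEJ at each visit. Writing d for change from Day 0, dPD = dCAL + dGM-CEJ. A PD-only site has dPD ≥ 2 and, in whole millimeters, dCAL ≤ 1. Hence dGM-CEJ = dPD − dCAL ≥ 2 − 1 = 1 mm, a coronal shift under the protocol's sign convention. Enumerating PD from 1 to 10 mm and GM-CEJ from −6 to +5 mm at two visits gives 1578 PD-only combinations. The smallest GM-CEJ rise among them is 1 mm, with no exception.

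**2. What the identity does not say.** The record dPD = 2, dGM-CEJ = 1 has dCAL = 1, so half of the PD rise is recorded attachment loss. Rounding down widens the range. A recorded rise of 2 means a true PD rise between 1 and 3 mm, and a recorded shift of 1 means a true shift between 0 and 2 mm. The true CAL change then lies between 1 − 2 = −1 and 3 − 0 = +3 mm.

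**3. Measurement error with no true change.** The documents give no error SD, so a range was assumed: normal error on each reading, rounding down, true PD uniform on 1–4 mm and true GM-CEJ uniform on 0–3 mm. Results are percentages of sites.

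| Assumed SD (mm) | PD-only | CAL rise ≥ 2 mm |
|---|---|---|
| 0.3 | 0.02% | 3.0% |
| 0.5 | 0.6% | 9.0% |
| 0.7 | 2.1% | 15.6% |
| 1.0 | 4.5% | 23.4% |

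Error alone therefore produces some PD-only sites, and produces CAL sites more often.

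**4. Possible effect on the comparison (all rates assumed).** Let c be the proportion of subjects with a CAL event and q the proportion with a PD-only event among the rest. The composite proportion is c + q(1 − c).

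| Scenario | c, placebo / active | q, placebo / active | Composite, placebo / active | CAL odds ratio | Composite odds ratio |
|---|---|---|---|---|---|
| A: rinse does not affect PD-only events | 5% / 10% | 5% / 5% | 9.75% / 14.5% | 2.11 | 1.57 |
| B: rinse halves PD-only events | 5% / 10% | 10% / 5% | 14.5% / 14.5% | 2.11 | 1.00 |
| C: as B, equal CAL events | 5% / 5% | 10% / 5% | 14.5% / 9.75% | 1.00 | 0.64 |

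For scenario B, placebo is 0.05 + 0.10 × 0.95 = 0.145 and active is 0.10 + 0.05 × 0.90 = 0.145. The CAL odds ratio is (0.10/0.90)/(0.05/0.95) = 2.11. In A the effect is diluted, in B it is offset, and in C the rinse looks protective with no difference in CAL events.

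**The case against.** An either/or rule is a defensible, sensitive choice for safety monitoring. Protocol 3.2.1 cites a source for the 2 mm criterion, and mucosal inflammation is itself a safety concern, so a PD rise from swelling is not irrelevant. Every recorded CAL rise of 2 mm or more is already an event, so no such loss goes unflagged. Protocol 12.1 plans no formal testing in the primary safety analysis, and SAP 8.2 attaches no decision rule to its odds ratios. SAP 9.3.3 compares CAL change between arms at Day 28 and lists site-level values. If the rinse has no effect on the margin, randomisation should balance PD-only events. Neither document says how many sites make a subject an event. Under an any-site rule, with at least 20 × 6 = 120 sites treated as independent and the error SDs assumed above, 97% or more of subjects would be flagged by CAL error alone, which would leave little room for PD-only subjects.

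Most of this stands. It supports keeping the composite, and it shows that the effect could be small. It does not supply the missing split. SAP 9.3.3 covers mean change rather than 2 mm events and omits Day 14, and listings are not a comparison by arm. Balanced PD-only events still dilute the odds ratio, as in scenario A.

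A reader might infer that PD-only events are swelling and not attachment loss. Steps 2 and 3 rule that out: the 1 mm shift is certain only in the recorded values. A reader might also infer that the whole safety outcome is confounded and should be redefined on CAL alone. The CAL limb is unaffected by true margin position. In a randomised comparison the issue is a component that may respond to treatment through another route, which is not confounding in the strict sense. CAL is also the noisier measure, because it combines two rounded readings. Nothing in the documents shows the composite to be an error.

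**Conclusion.** The point holds as a reporting gap. On the protocol's own formula, every site that qualifies on PD alone carries a recorded coronal margin shift of at least 1 mm, and that part of the outcome can move with the rinse's intended effect. Because SAP 8.2 compares arms only on the composite, its odds ratio cannot be attributed to attachment or to margin position.

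The identity is exact for whole-millimeter readings judged site by site. The size of any dilution or offset is unknown, because the documents give neither CAL nor PD-only rates and do not state the number of sites that define an event. The odds ratios above rest on assumed rates and show only what is possible. That the rinse would lower PD-only events is plausible from the MGI definitions, but the documents do not show it.

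**What to change.** Keep the protocol's composite definition. In SAP 8.2, add a table by arm and visit with three rows, all using the same subject-level site rule:

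- CAL increase of 2 mm or more;
- PD increase of 2 mm or more without a CAL increase of 2 mm or more, labelled PD-only and not swelling, since it can include attachment loss or error;
- the composite as now defined.

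Repeat the planned generalized linear mixed model for CAL events as a sensitivity analysis, and state that any composite odds ratio will be interpreted alongside the CAL result.

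No new data are needed: PD and GM-CEJ are already recorded at Baseline, Day 14 and Day 28. The protocol's outcome definition is unchanged. The cost is one more table and one more model with unadjusted p-values. The CAL result will be noisier, because CAL combines two rounded readings, so it should inform the reading of the composite and not replace it.
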